7.3.3 Exploratory Aims

Repeated measures analyses, using generalized linear mixed models, will be used to describe change in preferences over time and the relationship to clinical characteristics with a particular focus on evaluating the influence of response (e.g. remission) on preferences. Performance of the BWS survey will be evaluated including convergent validity, within-set dominated pairs, and attribute dominance.^{21,47} We will use frequency analysis to describe the strength of aggregate preferences for outcomes, and differences by age, race, gender, and clinical response.¹⁹ We will perform exploratory, hypothesis-generating analyses to compare within-person changes in preferences across timepoints, the relative stability of betas for attributes over time, and explore associations between preferences, decisional outcomes^{8,29-31}, patient-reported symptoms,³⁵ health-related quality of life³⁴, and provider perceptions. These analyses are exploratory as our sample size is relatively small. These exploratory analyses will inform future studies.

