4.3.4 Participant Recruitment and Stratification

For the pilot testing, recruitment of patients will be stratified into the following 3 groups:

Aggressive lymphomas: 20 patients

Acute leukemias: 20 patients

Myeloma, Chronic lymphocytic leukemia (requiring treatment), chronic myeloid leukemia: 10 patients

We will target a population that exceeds the following diversity thresholds: 30% non-white race, 50% female, 25% rural.

For the qualitative interviews, recruitment of patients will be stratified into the following 2 groups:

1. Those participants who believe that “Living longer” is the most important attribute (n=10),

and

2. Those participants who believe another attribute is the most important attribute (n=10).

Recruitment of clinicians will be as follows:

Oncology clinicians (including physicians, advanced practice providers, nurse navigators): 2-5

Palliative Care clinicians (including physicians, advanced practice providers, nurse navigators): 2-5

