4.3.8 Qualitative Interviews

Patients:

The qualitative interview will establish content validity of the BWS by cognitive interviews that will explore patients understanding of the content of the BWS.

Specific domains to be covered will include:

- Cognitive interview to evaluate patient understanding of each of the questions asked within the BWS
- subjective value of potential outcomes including attributes elicited in BWS
- patient understanding of how preferences influenced treatment decisions including elicitation of important factors in the decision (if applicable),
- expected outcomes,
- additional attributes not included in the BWS, and
- preferences for potential interventions to improve preference elicitation and decision-making.

In addition to open ended questions as part of the interview, patients will complete a digit span test to test working memory and recall.

The follow-up qualitative interview will cover the same content as the first interview in addition to asking participants to reflect upon how their experience has changed over the time period between interviews.

Interviews with clinicians will explore barriers and facilitators of implementation of surveys to capture patient values and preferences. There is no follow-up interview with clinicians. Clinicians will not complete the Digit span test.

Interviews will be recorded to allow for qualitative analysis. Transcripts of the interviews will be made. The interviews should take about 30 minutes to complete. Following the interview a codebook will be created with emerging themes to allow for qualitative analysis similar to previous studies.¹¹

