7.2 Sample Size and Accrual

Our primary objective is to establish content validity of the BWS survey. Based on established guidelines, 7-10 participants are needed to establish content validity of survey items in cognitive interviews.⁴¹⁻⁴³ As we will be stratifying patients for cognitive interviews into 2 groups, we will have 10 participants per stratification to ensure saturation in both.

Based on our prior data, we anticipate that we will have a 3:1 split between patients who value living longer most and those who value another attribute most. Therefore, we will need to recruit at least 40 patients to have 10 patients who value another attribute most to participate in cognitive interviews. Accounting for variability and drop out, we will plan to recruit 50 patients total to be able to recruit 10 patients in this group.

10 clinicians will provide for saturation for qualitative interviews.

This study was not designed to be powered to evaluate secondary endpoints or exploratory endpoints.

We expect to accrue up to 50 patients over the time of the study. We see over 500 new patients with hematologic malignancies per year within the division of hematology.

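### Interview exposure depends on the top BWS attribute (about 80% versus 27% at the planned split), and section 7.3.3 analyses preference change without accounting for it

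*Combined protocol and SAP*

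**What the plan says.** **Selection.** Sections 4.3.3 and 4.3.4 pick interviewees purposively from the BWS result: ten who put living longer first and ten who put something else first. Section 7.2 says "we will have 10 participants per stratification to ensure saturation in both". It also says "we anticipate that we will have a 3:1 split between patients who value living longer most and those who value another attribute most", and "we will plan to recruit 50 patients total".

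**Content and timing of interviews.** Section 4.3.8 lists, among the topics, the "subjective value of potential outcomes including attributes elicited in BWS" and how preferences fed into the treatment decision. Section 4.3.3 places the first interview within 14 days of the decision, with a further 14 days allowed, and a second about three months after the first. The second also asks patients to reflect on what has changed.

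**Repeat BWS.** Sections 4.3.2, 4.3.6 and 4.3.7 give six longitudinal assessments (LA1 after the clinic visit, then five more at two-week intervals) and up to seven extended assessments (EA) at three-month intervals. Table 5.1 also marks the BWS in the Qualitative Interviews column.

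**Analysis.** Section 7.3.3 uses generalized linear mixed models for change in preferences, with the emphasis on clinical response. It will also "compare within-person changes in preferences across timepoints" and explore how preferences relate to decisional outcomes, symptoms and quality of life. Interview status is not mentioned. The section labels these analyses exploratory.

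**The concern.** The interviews ask patients to think aloud about the same attributes that the BWS measures, and about the decision that the regret, conflict and communication scales ask about. Such a conversation could shift or stabilise later answers. Who has it depends on the quantity being followed over time, the top-ranked attribute, and most follow-up comes afterwards.

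An analysis that ignores interview status would then mix two things: change that happens with disease and treatment, and change prompted by the study's own interviews. Describing preference change is a stated aim (section 4.1.1), section 7.3.3 expects the results to guide later studies, and section 7.4 sends the data to a shared repository.

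**Working it through.** **1. The plan's own figure.** Section 7.2 states "we will need to recruit at least 40 patients to have 10 patients who value another attribute most". With one patient in four in that group, N = 10/0.25 = 40, so the figure reproduces. The step to 50 is explained only by "Accounting for variability and drop out". No rate is given; 1 − 40/50 = 20% is implied.

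**2. Expected interview share by group at N = 50.**
- Another attribute first: 50 × 0.25 = 12.5 patients; 10/12.5 = 80.0% interviewed, 2.5 not.
- Living longer first: 50 × 0.75 = 37.5 patients; 10/37.5 = 26.7% interviewed, 27.5 not.
- Difference: 53.3 percentage points.

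**3. Range of the split.** For a Binomial(50, 0.25) count, the central 95% range is 7 to 19 patients in the other-attribute group.
- At 7, all are interviewed: 7/7 = 100% versus 10/43 = 23%, a difference of 77 points.
- At 19: 10/19 = 53% versus 10/31 = 32%, a difference of 20 points.

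The imbalance has the same direction throughout.

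**4. How much follow-up comes after the first interview.** There are 6 + 7 = 13 post-decision BWS assessments. Take the worst case: LA1 on the day of the decision and the interview on the last permitted day, day 28. LA2 falls on day 14, LA3 on day 28 (a tie) and LA4 on day 42. LA4 to LA6 (3) and EA1 to EA7 (7) are then strictly later, so at least 10 of 13 follow the interview, or 11 if LA3 is completed after it.

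**5. What an interview effect would do if ignored.** Let d be the average shift that an interview causes in a later answer, the same in both groups. Compare a pre-interview record with a post-interview one, with all 20 interviews done and no dropout.
- Pooled change over time: (20/50) × d = 0.40d.
- Difference in change between the two groups: (0.800 − 0.267) × d = 0.53d. Over the range in step 3 the multiplier runs from 0.77 to 0.20.

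The documents give no value for d. As an illustration only, let d be a change in the probability of switching top attribute:

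| Assumed d (points) | Pooled change (0.40d) | Group difference (0.53d) |
|---|---|---|
| 0 | 0 | 0 |
| 15 | 6 | 8 |
| 30 | 12 | 16 |

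**6. Can the effect be separated?** The expected table is 10 and 2.5 (other attribute: interviewed, not) and 10 and 27.5 (living longer: interviewed, not). The correlation between group and interview status is (10 × 27.5 − 2.5 × 10)/√(12.5 × 37.5 × 20 × 30) = 250/530.3 = 0.47. The variance inflation from fitting both terms is 1/(1 − 0.47²) ≈ 1.29. This treats interview status as fixed per patient, so it is approximate for a time-varying term.

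**The case against.** The strongest objection is that section 7.3.3 does not list a comparison of change by baseline top attribute. Its named comparisons are across timepoints, by clinical characteristics and response, and by age, race and gender. This stands. A reader might infer that any interview effect will show up as preference-dependent change, but the documents do not support that. In the pooled analyses that are listed, the effect would appear as change over time (0.40d). The 0.53d applies only if preferences enter as the top attribute, for example in the planned associations with decisional outcomes; there d is the interview's effect on that outcome.

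Nothing in the documents shows that interviews change BWS answers, and all 50 patients are prompted to reflect simply by repeating the BWS. This also stands, so the point is conditional. Even an assumed 15-point effect gives an 8-point group difference. The standard error of that difference, √(p(1 − p)(1/12.5 + 1/37.5)), is about 10 points at an assumed switching rate of 10% and about 16 points at 50%. The bias could well be smaller than the noise.

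Two further inferences go too far. One is that the models cannot separate interview effects from other change: about 30 of 50 patients are not interviewed, so separation is possible, though weak in the other-attribute group. The other is that the mark in Table 5.1 means extra, interviewer-led BWS data. It may only mean that the BWS is at hand as material for the cognitive interview; the table gives neither mode nor use.

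The exploratory label lowers the stakes. It does not remove the gap, because the plan itself creates the unequal exposure and can easily record it.

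**Conclusion.** The concern holds as a conditional, modest weakness in an exploratory aim. By design, interview exposure is unequal by top attribute, at about 80% versus 27% expected, and it precedes at least 10 of the 13 post-decision assessments. Section 7.3.3 does not account for it. An interview effect d would add about 0.40d to pooled change and about 0.53d to any comparison by baseline top attribute.

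These figures rest on the plan's 3:1 split, ten completed interviews per group, no dropout, interviews held within their window and an effect common to both groups. The size of d is unknown and may be zero, so no bias of a particular size is shown. The primary content-validity aim is unaffected.

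**What to change.** In section 7.3.3:

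1. Add to the mixed models a time-varying term for whether the patient had been interviewed before the assessment, fitted together with baseline top attribute as defined by the BWS used to select interviewees.
2. As a sensitivity analysis, report change by interview status within the living-longer group (about 10 interviewed, 27 not). An analysis of all never-interviewed patients is a poor substitute. Only 2 to 3 of them would be other-attribute patients, so about 92% (27.5/30) would come from one group, and a different result could reflect composition alone.
3. State whether the BWS marked under Qualitative Interviews in Table 5.1 is re-administered. If it is, keep those records out of the longitudinal dataset and the completion counts.

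The cost is one or two extra parameters, a variance inflation of about 1.29 for the interview and group terms, and the interview date carried into the analysis dataset. The documents do not say that this date is stored as a variable. Patient procedures do not change.

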7.4 Data Management/Audit

Data will be stored on a shared, Oracle-Based framework which provides a highly secure IT environment, utilizing a secure authentication mechanism, the Transport Layer Security (TLS) system. This security mechanism supports encryption in both directions (to and from the website) across all devices including mobile devices such as smartphones. Backup files of all data will be included on this server. Only those trained to work with sensitive data will have access to the server. This project will have a specific folder on the server that will require password access for all users.

Data collection will be done by the study team. Study personnel will input data from patient interview or chart review into the database.

The Principal Investigator will provide continuous monitoring of subject safety in this trial with periodic reporting to the Data and Safety Monitoring Committee (DSMC).

The Principal Investigator will provide continuous monitoring of subject safety in this trial with periodic reporting to the Data and Safety Monitoring Committee (DSMC). Data sources included in this study will include data from medical records, questionnaires, and audio recordings. Data will be extracted from medical records by trained clinical research assistants and placed in a study-specific database per the protocol. Questionnaires will be delivered electronically. Data will be automatically transferred to the database. Audio recordings will be produced during the qualitative interviews and will be transcribed by trained personnel. The transcripts will be transferred electronically into the secure database. Data will undergo periodic review by the PI and the project manager for integrity.

Meetings/teleconferences will be held at a frequency dependent on study accrual. These meetings will include the investigators as well as protocol nurses, clinical research associates, regulatory associates, data managers, biostatisticians, and any other relevant personnel the principal investigators may deem appropriate. At these meetings, the research team will discuss all issues relevant to study progress, including enrollment, safety, regulatory, data collection, etc.

The team will produce summaries or minutes of these meetings. These summaries will be available for inspection when requested by any of the regulatory bodies charged with the safety of human subjects and the integrity of data including, but not limited to, the Office of Human Research Ethics (OHRE) Biomedical IRB, the Oncology Protocol Review Committee (PRC) or the North Carolina TraCS Institute Data and Safety Monitoring Board (DSMB).

As an investigator initiated study, this trial will also be audited by the Lineberger Cancer Center audit committee every six or twelve months, depending on the participation of affiliate sites.

Once complete, data will be de-identified and transferred to the Palliative Care Research Consortium (PCRC) repository for dissemination.

8.0 STUDY MANAGEMENT

8.1 Institutional Review Board (IRB) Approval and Consent

It is expected that the IRB will have the proper representation and function in accordance with federally mandated regulations. The IRB should approve the consent form and protocol.

In obtaining and documenting informed consent, the investigator should comply with the applicable regulatory requirement(s), and should adhere to Good Clinical Practice (GCP) and to ethical principles that have their origin in the Declaration of Helsinki.

Before recruitment and enrollment into this study, the patient will be given a full explanation of the study and will be given the opportunity to review the consent form. Each consent form must include all the relevant elements currently required by the FDA Regulations and local or state regulations. Once this essential information has been provided to the patient and the investigator is assured that the patient understands the implications of participating in the study, the patient will be asked to give consent to participate in the study by signing an IRB-approved consent form.

Prior to a patient's participation in the trial, the written informed consent form should be signed and personally dated by the patient and by the person who conducted the informed consent discussion.

8.2 Required Documentation

Before the study can be initiated, the following documentation must be provided to the Clinical Protocol Office (CPO) at the University of North Carolina.

- A copy of the official IRB approval letter for the protocol and informed consent
- CVs and medical licensure for the principal investigator and any associate investigators who will be involved in the study
- A copy of the IRB-approved consent form

8.3 Registration Procedures

Patient enrollment will be tracked in a secure database as outlined above.

8.4 Adherence to the Protocol

Except for an emergency situation in which proper care for the protection, safety, and well-being of the study patient requires alternative treatment, the study shall be conducted exactly as described in the approved protocol.

8.4.1 Emergency Modifications

UNC investigators may implement a deviation from, or a change of, the protocol to eliminate an immediate hazard(s) to trial subjects without prior UNC IRB approval.

For any such emergency modification implemented, a UNC IRB modification form must be completed by UNC Research Personnel within five (5) business days of making the change.

8.4.2 Single Patient/Subject Exceptions

We will not allow single patient exceptions in the study. Any request to enroll a single subject who does not meet all the eligibility criteria of this study requires the approval of the UNC Principal Investigator and the UNC IRB.

8.4.3 Other Protocol Deviations/Violations

According to UNC's IRB, a protocol deviation is any unplanned variance from an IRB approved protocol that:

- Is generally noted or recognized after it occurs
- Has no substantive effect on the risks to research participants
- Has no substantive effect on the scientific integrity of the research plan or the value of the data collected
- Did not result from willful or knowing misconduct on the part of the investigator(s).

An unplanned protocol variance is considered a violation if the variance meets any of the following criteria:

- Has harmed or increased the risk of harm to one or more research participants.
- Has damaged the scientific integrity of the data collected for the study.
- Results from willful or knowing misconduct on the part of the investigator(s).
- Demonstrates serious or continuing noncompliance with federal regulations, State laws, or University policies.

If a deviation or violation occurs please follow the guidelines below:

Protocol Deviations: UNC personnel will record the deviation in OnCore® (or other appropriate database set up for the study), and report to any sponsor or data and safety monitoring committee in accordance with their policies. Deviations should be summarized and reported to the IRB at the time of continuing review.

Protocol Violations: Violations should be reported by UNC personnel within one (1) week of the investigator becoming aware of the event using the same IRB online mechanism used to report UPIRSO.

Unanticipated Problems Involving Risks to Subjects or Others (UPIRSO):

Any events that meet the criteria for "Unanticipated Problems" as defined by UNC's IRB (see section 6.1) must be reported by the Study Coordinator using the IRB's web-based reporting system. The PI will be responsible for reporting UPIRSO to the PCRC and the NINR.

8.5 Amendments to the Protocol

Should amendments to the protocol be required, the amendments will be originated and documented by the Principal Investigator at UNC. It should also be noted that when an amendment to the protocol substantially alters the study design or the potential risk to the patient, a revised consent form might be required.

The written amendment, and if required the amended consent form, must be sent to UNC's IRB for approval prior to implementation.

8.6 Record Retention

Study documentation includes all Case Report Forms, data correction forms or queries, source documents, Sponsor-Investigator correspondence, monitoring logs/letters, and regulatory documents (e.g., protocol and amendments, IRB correspondence and approval, signed patient consent forms).

Source documents include all recordings of observations or notations of clinical activities and all reports and records necessary for the evaluation and reconstruction of the clinical research study.

Government agency regulations and directives require that all study documentation pertaining to the conduct of a clinical trial must be retained by the study investigator. In the case of a study with a drug seeking regulatory approval and marketing, these documents shall be retained for at least two years after the last approval of marketing application in an International Conference on Harmonization (ICH) region. In all other cases, study documents should be kept on file until three years after the completion and final study report of this investigational study.

8.7 Obligations of Investigators

The Principal Investigator is responsible for the conduct of the clinical trial at the site in accordance with Title 21 of the Code of Federal Regulations and/or the Declaration of Helsinki. The Principal Investigator is responsible for personally overseeing the treatment of all study patients. The Principal Investigator must assure that all study site personnel, including sub-investigators and other study staff members, adhere to the study protocol and all FDA/GCP/NCI regulations and guidelines regarding clinical trials both during and after study completion.

The Principal Investigator at each institution or site will be responsible for assuring that all the required data will be collected and entered onto the Case Report Forms. Periodically, monitoring visits will be conducted and the Principal Investigator will provide access to his/her original records to permit verification of proper entry of data. At the completion of the study, all case report forms will be reviewed by the Principal Investigator and will require his/her final signature to verify the accuracy of the data.

8.8 Data and Safety Monitoring Plan

The Principal Investigator will provide continuous monitoring of subject safety in this trial with periodic reporting to the UNC Lineberger Data and Safety Monitoring Committee (DSMC).

Monitoring Procedures:

Meetings/teleconferences will be held at a frequency dependent on study accrual. These meetings will include the investigators as well as protocol nurses, clinical research associates, regulatory associates, data managers, biostatisticians, and any other relevant personnel the principal investigators may deem appropriate. At these meetings, the research team will discuss all issues relevant to study progress, including enrollment, safety, regulatory, data collection, etc.

The team will produce summaries or minutes of these meetings. These summaries will be available for inspection when requested by any of the regulatory bodies charged with the safety of human subjects and the integrity of data including, but not limited to, the Office of Human Research Ethics (OHRE) Biomedical IRB, the Oncology Protocol Review Committee (PRC) or the North Carolina TraCS Institute Data and Safety Monitoring Board (DSMB).

The UNC LCCC Data and Safety Monitoring Committee (DSMC) will review the study once the protocol is finalized. Based on the “minimal risk” nature of the study (behavioral, non-therapeutic trial), it is anticipated that the DSMC will review the study on an annual basis. The UNC PI will be responsible for submitting the following information for review: 1) safety and accrual data including the number of subjects treated; 2) significant developments reported in the literature that may affect the safety of participants or the ethics of the study; 3) preliminary response data; and 4) summaries of team meetings that have occurred since the last report. Findings of the DSMC review will be disseminated by memo to the UNC PI, PRC, and the UNC IRB and DSMB. Summaries will also be made available for review by the PCRC and the National Institute of Nursing Research (NINR). The PI will be responsible for submitting summaries to the PCRC and the NINR. In accordance with our institutional guidelines, studies deemed “minimal risk” will not be audited.

Minimization of Risk:

Some questions in the patient questionnaires, interviews or survey could create emotional distress or confusion. Patients will be instructed that the questionnaires are for research purposes only and any problem or symptom should also be reported to their physician or nurse.

We do not anticipate any breach of confidentiality although recognize that a breach in confidentiality may result in psychological, social, or economic harm to a patient if the details of the medical record become available to others. Any information about the participants obtained from this research will be kept as confidential as possible. All data obtained will be stored on a secure server.

